8. SAFETY ANALYSES

The safety analyses will be based on the mITT population.

8.1. Adverse Events Analyses

Adverse events analyses including the analysis of adverse events (AEs), Serious (SAEs) and other significant AEs will be based on GSK Core Data Standards. The details of the planned displays are provided in [Appendix 11: List of Data Displays](#).

8.2. Adverse Events of Special Interest Analyses

A comprehensive list of MedDRA terms based on clinical review will be used to identify each type of event. SRT, safety review team, has decided the Infective Pneumonia SMQ will be used to identify AESI. The details of the planned displays are provided in [Appendix 11: List of Data Displays](#).

8.3. Clinical Laboratory Analyses

Laboratory evaluations including the analyses of Chemistry laboratory tests, Haematology laboratory tests, Urinalysis, and liver function tests will be based on GSK Core Data Standards. The details of the planned displays are in [Appendix 11: List of Data Displays](#). The blood biomarkers, plasma fibrinogen and serum C-reactive protein, will be in the efficacy outputs.

8.4. Other Safety Analyses

The analyses of non-laboratory safety test results including ECGs and vital signs will be based on GSK Core Data Standards, unless otherwise specified. The details of the planned displays are presented in [Appendix 11: List of Data Displays](#). Summaries of spirometry will also be created.

9. PHARMACOKINETIC ANALYSES

9.1. Primary Pharmacokinetic Analyses

9.1.1. Endpoint / Variables

9.1.1.1. Drug Concentration Measures

Refer to [Appendix 5: Data Display Standards & Handling Conventions \(Section 12.5.3 Reporting Standards for Pharmacokinetic\)](#)

9.1.1.2. Derived Pharmacokinetic Parameters

Pharmacokinetic parameters will be calculated by standard non-compartmental analysis per current working practices and using the currently supported version of WinNonlin. All calculations of non-compartmental parameters will be based on actual sampling times. The pharmacokinetic parameters listed below will be determined from the blood concentration-time data on Day 1 and Day 14, as data permits.

Parameter	Parameter Description
AUC(0-t)	Area under the concentration-time curve from time zero to the time of the last quantifiable concentration (C(t)) will be calculated using the linear trapezoidal rule for each incremental trapezoid and the log trapezoidal rule for each decremental trapezoid.
C _{max} *	Maximum observed concentration, determined directly from the concentration-time data.
t _{max}	Time to reach C _{max} , determined directly from the concentration-time data.
t _{last}	Time of last quantifiable concentration

NOTES:

- Additional parameters may be included as required.

Unless otherwise specified, endpoints / variables defined in Section 9.1.1 will be summarised using descriptive statistics, graphically presented (where appropriate) and listed.

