  - 4. Sputum induction (and associated VOC measurement and safety spirometry) at visit 1 is only necessary if participant unable to give sample at visit 0. Where the participant is judged by the investigator to have a borderline sputum NETs level (<0.5 units/ml) at visit 0, they will be invited to give a second sputum sample on visit 1 to re-assess eligibility.

  - 5. VOC measurements should be undertaken at the following timepoints at this visits: prior to sputum induction, and 4 hours post dose
  - 6. Hepatitis B (HBsAg) and Hepatitis C (HepC antibody) testing is required. If testing otherwise performed within 3 months prior to the first dose of study treatment, testing at screening is not required. Hepatitis C Ribonucleic acid (RNA) testing is optional; however a confirmatory negative Hepatitis C RNA test must be obtained, to be able to enroll participants with positive Hepatitis C antibody due to prior resolved disease.
  - 7. At visits 2 and 4, PK samples should be collected at the following time-points: pre-dose, 0.5, 1, 2 and 4 hours post-dose.
  - 8. At visit 3 only a pre-dose PK sample should be collected.
  - 9. Agreeing to genetic sample consent is not required for overall study participation. Informed consent for genetic sample must be obtained prior to taking sample.
  - 10. Pregnancy testing only required for women of child bearing potential (WOCBP). A positive urine pregnancy test requires confirmation with a serum pregnancy test.

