# 4. OBJECTIVES AND ENDPOINTS

	Objectives		Endpoints
	participants with COPD	•	Spirometry Clinical Laboratory Assessments (hematology, clinical chemistry, urinalysis)
•	To assess the effects of danirixin HBr 35mg twice daily on NETosis- associated biomarkers in sputum and	•	Change from baseline in sputum resistin levels
	peripheral blood	•	Change from baseline in the ratio of sputum NETs to sputum neutrophils
		•	Change from baseline in sputum elastase activity
		•	Change from baseline in peripheral blood neutrophil NET formation (DNA release, microscopy)
•	Characterise the population pharmacokinetic (PK) profile of approximately 14 days of dosing of danirixin HBr 35mg twice daily in participants with COPD	•	Model specific PK parameters of danirixin (e.g., oral clearance, oral steady- state volume of distribution).
Ex	ploratory		
•	To explore the relationships between NETs formation and lung microbiome composition	•	Characterize sputum microbiome composition and diversity
•	To explore volatile organic compound (VOC) profile in participants with COPD	•	Characterize relationship between lung microbiome and exhaled volatile organic compounds (VOCs) in stable COPD To explore variability of exhaled VOCs
•	To explore the effects of danirixin HBr 35mg twice daily on neutrophil activity and exploratory biomarkers	•	Changes from baseline in ex-vivo neutrophil phagocytosis of bacteria by flow cytometry Changes in exploratory urine, sputum and blood biomarkers (e.g. plasma fibrinogen, serum C-reactive protein, serum IL-8 or sputum mucin)
•	To explore the effects of an App on adherence to treatment with danirixin or placebo	•	Characterize treatment adherence in relation to monitoring via App and explore relationship to PK parameters

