# 7. TREATMENTS

Study treatment is defined as any investigational treatment(s), marketed product(s), placebo, or medical device(s) intended to be administered to a study participant according to the study protocol.

Dosage formulation:	White Film coated tablets (oval shaped). Refer to Investigator's Brochure for presentation and excipients	White Film coated tablets (oval shaped). Refer to Investigator's Brochure for presentation and excipients
Unit dose strength(s)/Dosage level(s):	35mg HBr	N/A
Route of Administration	Oral	Oral
Dosing instructions:	One tablet to be taken twice daily with food	One tablet to be taken twice daily with food
Packaging and Labelling	Study Treatment will be provided in a High- density polyethylene (HDPE) bottle with desiccant. Each bottle will be labelled as required per country requirement.	Study Treatment will be provided in a HDPE bottle with desiccant. Each bottle will be labelled as required per country requirement.
Manufacturer	GSK	GSK

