2. SUMMARY OF KEY PROTOCOL INFORMATION

2.1. Changes to the Protocol Defined Statistical Analysis Plan

Protocol	Reporting & Analysis Plan	
Statistical Analysis Plan	Statistical Analysis Plan	Rationale for Changes

 Enrolled - All participants who sign informed consent 	
 Enrolled - All participants who sign informed consent and for whom a record exists on the study database 	
 Align with standard Enrolled population definition.

 Randomised 	
 mITT population defined to be used for selected displays 	
 Used for key displays

 Primary completer 	
 Population definition refined 	
 To allow for missing data and increase clarity

 Safety 	
 mITT population used for safety reporting 	
 Safety population not required.

 PK population 	
 PK population defined 	
 Used for PK displays

 Endpoint - Model specific PK parameters of danirixin (e.g., oral clearance, oral steady state volume of distribution). 	
 Danirixin concentration and standard pharmacokinetic (PK) parameters for danirixin (e.g. AUC, Cmax, tmax) 	
 Updated due to small number of participants with PK data

 Endpoints - serum IL-8 or sputum mucin 	
 Removed 	
 Not collected

 Primary analysis Bayesian 	
 Primary analysis Frequentist 	
 The primary analysis has been simplified as the historical data could not be used as a prior.

 Modified Primary Completer 	
 Population defined 	
 Defined to allow for a sensitivity around the definitions of quality for the samples

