NDAY: For deriving the nominal day which is the planned day, DAY specific information is not available in EXPOSURE dataset. VISIT variable and the time and events table might have to be taken into account to find the exact plan of events.

NOMT: It is twice daily dosing with inter-dose interval given to be 12 hours. Therefore, to find the planned time of event since the first dose in hours, again the VISIT variable and time and events will have to be considered.

NOMTLD: In case of PK_GSK1325756 records, the planned time point variable will give the value of this variable for all the post-dose records. For the pre-dose records, this variable will have missing values since there is no fixed time point since the previous dose for pre-dose records.

RTFD: The time difference between the first dose of the subject and the current dose (when LABEL=DOSE_GSK1325756) should be calculated in hours. The time difference

between the first dose of the subject and the PK sample collection time (when LABL=PK_GSK1325756) should be calculated in hours.

RTLD: The latest dose prior to the PK sample collection time will have to be found out and the time difference between that dose and the PK sample collection time will be calculated in hours.

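### The only AUC the SAP names stops at 4 h of a 12 h dosing interval, and no committed analysis reports oral clearance, although the scheduled Day 14 pre-dose sample would support both a full-interval AUC and CL/F

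*SAP*

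**What the plan says.** **Sampling.** Footnote 7 to the Schedule of Activities (Protocol section 2, repeated in SAP Appendix 2) reads: "At visits 2 and 4, PK samples should be collected at the following time-points: pre-dose, 0.5, 1, 2 and 4 hours post-dose". Visits 2 and 4 are Days 1 and 14. Day 7 has a pre-dose sample only.

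**Dosing.** Protocol section 7: "One tablet to be taken twice daily with food". The population PK dataset notes in SAP 12.9.1.5 add: "It is twice daily dosing with inter-dose interval given to be 12 hours".

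**Endpoint.** Protocol section 4 gives the secondary PK endpoint as "Model specific PK parameters of danirixin (e.g., oral clearance, oral steady- state volume of distribution". SAP 2.1 replaces it with concentrations and standard PK parameters, for the stated reason "Updated due to small number of participants with PK data". SAP 2.2 keeps the objective of characterising the population PK profile over about 14 days of twice-daily dosing.

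**Analysis.** SAP 9.1.1.2 lists four non-compartmental parameters for Days 1 and 14:
- AUC(0-t), the "Area under the concentration-time curve from time zero to the time of the last quantifiable concentration"
- Cmax, the "Maximum observed concentration, determined directly from the concentration-time data"
- tmax
- tlast

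A note allows further parameters but names none. Protocol 10.3.3 already listed the same four. Both documents say that population PK modelling may be done, under a separate plan and outside the main study report (Protocol 10.3.3, SAP section 10).

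**The concern.** An AUC to the last quantifiable concentration measures exposure over the interval only if sampling runs to the end of the interval. Here it stops after one third. The area also depends on each participant's last usable sample: if the 4 h sample is missing or not quantifiable, the window is shorter, yet all values are pooled in Table 4.2.

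Oral clearance was the protocol's first example of the PK endpoint. It needs the AUC over a whole steady-state interval, or a fitted model. The SAP commits to neither. At stake is a descriptive secondary result: the study report would carry a partial exposure figure and no clearance, while the samples to do better are already scheduled. No primary or safety conclusion depends on it.

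**Working it through.** The documents give no figure for AUC coverage or clearance, so there is none to reproduce.

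**Inputs from the documents**
- Sampling times: 0, 0.5, 1, 2 and 4 h (Schedule of Activities, footnote 7).
- Interval: tau = 12 h (SAP 12.9.1.5).
- Half-life: the male contraception criterion in Protocol 6.1 equates 60 h with about 6 half-lives, so 60/6 = 10 h and ke = ln 2/10 = 0.0693 per h.
- AUC rule: linear when rising, logarithmic when falling (SAP 9.1.1.2).

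**Assumptions.** One-compartment oral model; ka 0.5, 1 or 2 per h. Neither is in the documents.

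**Step 1, time covered.** 4/12 = 33% at most by schedule.

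**Step 2, share of the area.** At steady state AUC(0-12) equals 1/ke in units of F x dose/V, so

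share = ke x ka/(ka - ke) x { (1 - e^(-4ke)) / [ke(1 - e^(-12ke))] - (1 - e^(-4ka)) / [ka(1 - e^(-12ka))] }.

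For ka = 1: 0.0693 x 1.0745 x (6.186 - 0.982) = 0.388.

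**Step 3, is Day 14 at steady state?** Dosing for 13 days before that visit is 13 x 24 = 312 h, about 31 half-lives. Yes. The concentration just before the dose therefore equals the one 12 h after it, if doses are 12 h apart.

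**Step 4, full-interval AUC from existing samples.** Place the pre-dose value at 12 h and apply the SAP's trapezoidal rule to 0, 0.5, 1, 2, 4 and 12 h. Divide by the true AUC(0-12).

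**Step 5, irregular previous dose.** Repeat Step 4 with the previous dose 10 h or 14 h before the Day 14 dose.

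Results at a 10 h half-life:

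| ka (per h) | AUC(0-4)/AUC(0-12) | Recovered, gap 12 h | Gap 10 h | Gap 14 h |
|---|---|---|---|---|
| 0.5 | 35.8% | 98.0% | 107.6% | 89.3% |
| 1 | 38.8% | 99.2% | 108.5% | 91.1% |
| 2 | 40.8% | 99.5% | 108.5% | 91.7% |

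**Sensitivity**
- With ka from 0.2 to 3 per h at 10 h, the share is 34-42%.
- Half-lives of 4 to 6 h give shares of 38-53%, but the documents offer no basis for them.
- Over half-lives of 4, 6 and 10 h with the three ka values, Step 4 recovers 96-99.5% when the gap is 12 h.
- At a 10 h half-life, a gap of 8 h or 16 h puts AUC(0-tau) off by about +19% or by -15 to -18%.
- At a 5 h half-life, a 2 h deviation costs +10 to +11% or -10 to -15%.

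**Step 6, effect on clearance.** CL/F = dose/AUC(0-tau), so its bias is the reciprocal. With a 12 h gap it is 1/0.995 to 1/0.980, or +0.5% to +2%. With a 2 h deviation it runs from 1/1.085 (-8%) to 1/0.893 (+12%).

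**The case against.** **The change was declared.** SAP 2.1 states the replacement and gives a reason other than the 4 h cut-off. Protocol 10.3.3 had already planned these four parameters, and clearance was a model-based example, never a planned non-compartmental output. This stands: a reader might infer that the endpoint was quietly lost because sampling is short, and the documents do not support that. But few participants is a reason not to fit a model. It does not prevent a per-participant CL/F.

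**AUC(0-t) is not the only exposure measure.** Correct. Cmax is listed, concentrations are summarised (Table 4.1) and troughs are plotted (Figures 4.5 and 4.6). It is only the sole AUC named.

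**The label is honest.** AUC(0-t) is defined as what it is, and tlast is reported beside it. A reader might infer that it will be set against the AUC(0-24) exposure margin in Protocol 3.3.1. That margin rests on earlier modelling, and neither document plans such a comparison.

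**Population PK could supply clearance.** It could, and SAP section 10 says the dataset will be generated. The modelling itself remains optional.

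**The substitution depends on home dosing.** This is the strongest point. SAP 12.9.1.5 says pre-dose records have no fixed time since the previous dose, and SAP 12.9.1.2 imputes missing dose times case by case. Protocol 7.6 promises clock times for clinic doses; for home doses it names tablet counts, start and stop dates and an optional app. High recovery therefore cannot be claimed without a timing rule.

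**It matters little.** The study was stopped early with 19 completers (SAP 3.2). That limits the importance, not the correctness.

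**Conclusion.** The point holds as a modest, inexpensive improvement. The one AUC named covers at most a third of the interval by schedule and, at the implied 10 h half-life, about 36-41% of the steady-state AUC(0-12). The PK objective is retained, but no committed analysis reports oral clearance, although the Day 14 samples support it.

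The shares rest on the assumed one-compartment model and ka range, and on a half-life inferred from a contraception window. The recovery also needs steady state and a previous dose close to 12 h earlier.

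Two stronger readings should be avoided. AUC(0-4) does not cover about half the interval: a share near half needs half-lives that the documents do not give. Nor would the remedy restore the whole protocol endpoint: steady-state volume stays out of reach because no terminal-phase samples are taken.

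**What to change.** In SAP 9.1.1.2:

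1. For Day 14, add AUC(0-tau) with tau = 12 h, using the pre-dose concentration as C(12 h), and CL/F = dose/AUC(0-tau).
2. State a timing rule in advance. Either calculate both only when the recorded time since the previous dose is within a stated tolerance of 12 h, or adjust the pre-dose value to 12 h by a stated method. The table above can guide the tolerance: 2 h costs about 8-11% at a 10 h half-life. Adjustment helps only in part, because an irregular gap also alters the 0 to 4 h samples.
3. Confirm where the time of the last home dose is recorded. The population PK dataset already requires it as actual time since last dose (RTLD); list it with the parameters.
4. Rename the existing area as partial AUC(0-4) over a common window on both days, and say how participants without a usable 4 h sample are handled.
5. If a 24 h figure is wanted, present 2 x AUC(0-12) as an approximation that assumes equal day and night intervals.
6. Footnote the reliance on steady state and on the reported home-dose time, and state that steady-state volume is not estimated.

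The cost is SAP wording and a few derived parameters, with no extra samples. The downside is that some participants may have no Day 14 AUC(0-tau), in a group that is already small. Committing to the population PK analysis would also deliver clearance, with more work.

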10. POPULATION PHARMACOKINETIC (POPPK) ANALYSES

PK data from this study may be combined with historic data for the purposes of population PK modelling which would be the subject of a separate analysis plan and would be presented separately from the main clinical study report (CSR).

To support this analysis a PopPK dataset will be generated. The details for the dataset specifications are provided in [Section 12.8 Appendix 9](#).

12. APPENDICES

12.1. Appendix 1: Protocol Deviation Management and Definitions for Per Protocol Population

12.1.1. Exclusions from Per Protocol Population

No per protocol analysis is defined in this study.

12.2. Appendix 2: Schedule of Activities

12.2.1. Protocol Defined Schedule of Events

Table 1 Schedule of activities

Procedure	Pre-Screening and Screening ¹		Treatment Period (14 days)			Follow-up Phone call	Unscheduled visit ²	Notes
	V0	V1	V2	V3	V4	V5		
Day	Day -30 to -1		D 1	D 7	D14	D 21	As required	
Assessment window				±1d	±1d	± 3d	As required	
Written, informed consent	X							
Inclusion and exclusion criteria	X							Recheck clinical status before randomization.
Demography, Medical history	X							
Baseline COPD assessment test (CAT) score	X							
Adverse event (AE)/Serious adverse event (SAE) review	X	←=====→				X	X	
Concomitant medication review	X	←=====→				X	X	
Full physical examination including height and weight	X						X	
Vital signs	X	X	X	X	X		X	
Volatile organic compound (VOC) measurement	X ³	X ^{3,4}	X ⁵	X ³	X ³		X	
Spirometry	X		X		X		X	
Induced Sputum Samples (including biomarker samples)	X	X ⁴	X	X	X		X	
Spirometry post-Sputum Induction	X	X ⁴	X	X	X		X	
Triplicate 12-lead ECG		X	X		X		X	
Chest X-ray (historical within 1 year acceptable)		X						
HIV, Hepatitis B and C screening		X ⁶						
Laboratory assessments (clinical chemistry including liver chemistries, haematology, biomarkers)		X	X		X		X	
Pharmacokinetic (PK) sample			X ⁷	X ⁸	X ⁷		X	See footnotes for timings of PK sampling
Genetic sample			X ⁹					Pre-dose (baseline) sample.
Urinary Pregnancy test (WOCBP only)		X ¹⁰	X ¹⁰		X ¹⁰		X ¹⁰	

Procedure	Pre-Screening and Screening ¹		Treatment Period (14 days)			Follow-up Phone call	Unscheduled visit ²	Notes
	V0	V1	V2	V3	V4	V5		
Urinalysis (including biomarker samples)		X	X		X		X	
Randomization			X					All baseline assessments at V2 should be completed prior to randomization
Study treatment			X	←→	X			
Dispense study medication			X					
Monitor IP compliance (via manual counting and App)			X	X	X			Digital App monitoring to begin at V2
Collect IP					X			

- The timing and number of planned study assessments, including safety, pharmacokinetic, pharmacodynamic/biomarker or other assessments may be altered during the course of the study based on newly available data (e.g., to obtain data closer to the time of peak plasma concentrations) to ensure appropriate monitoring.
- Any changes in the timing or addition of time points for any planned study assessments must be documented and approved by the relevant study team member and then archived in the sponsor and site study files, but will not constitute a protocol amendment. The IRB/IEC will be informed of any safety issues that require alteration of the safety monitoring scheme or amendment of the Informed consent form (ICF).
- Safety assessments should be performed in the following order where applicable/ possible: vital signs, ECG measurements, blood samples and spirometry.
 1. Screening visit is split into pre-screening on visit 0 and screening on visit 1 although the visits may be performed on the same day. This is to a) enable participants to potentially have more than one attempt at sputum induction for meeting eligibility and b) to only collect minimal screening data for subjects who fail on the basis of the elevated NETs since that is the key inclusion criteria that may not be known from medical records.
 2. Unscheduled visits may be used to collect information related to adverse events, for follow up of any safety assessments, and also to complete assessments where participants were not able to perform these within the visit window for any reason. It is not necessary to carry out all of the assessments listed under an unscheduled visit at a single visit; the assessments performed should be driven by the need for the visit.
 3. VOC measurement should be undertaken prior to sputum induction at these visits.
 4. Sputum induction (and associated VOC measurement and safety spirometry) at visit 1 is only necessary if participant unable to give sample at visit 0. Where the participant is judged by the investigator to have a borderline sputum NETs level (<0.5 units/ml) at visit 0, they will be invited to give a second sputum sample on visit 1 to re-assess eligibility.
 5. VOC measurements should be undertaken at the following timepoints at this visits: prior to sputum induction, and 4 hours post dose
 6. Hepatitis B (HBsAg) and Hepatitis C (HepC antibody) testing is required. If testing otherwise performed within 3 months prior to the first dose of study treatment, testing at screening is not required. Hepatitis C Ribonucleic acid (RNA) testing is optional; however a confirmatory negative Hepatitis C RNA test must be obtained, to be able to enroll participants with positive Hepatitis C antibody due to prior resolved disease.
 7. At visits 2 and 4, PK samples should be collected at the following time-points: pre-dose, 0.5, 1, 2 and 4 hours post-dose.
 8. At visit 3 only a pre-dose PK sample should be collected.
 9. Agreeing to genetic sample consent is not required for overall study participation. Informed consent for genetic sample must be obtained prior to taking sample.
 10. Pregnancy testing only required for women of child bearing potential (WOCBP). A positive urine pregnancy test requires confirmation with a serum pregnancy t

